6.2.5. Visit 5 (168 to 196 Days After Last Vaccination), Telephone Contact

- This telephone contact should occur approximately 6 months after the last Stage 1 study vaccination; this contact should be attempted for all subjects who have received at least 1 Stage 1 study vaccination, unless they have withdrawn consent.
- Contact the parent(s)/legal guardian or the subject by telephone.
- Complete the Study Visit/Telephone Contact AE Checklist to:
 - Inquire about SAEs, newly diagnosed chronic medical conditions, or AEs that resulted in evaluation at a medical facility since the last visit. Please refer to the SRM for additional details.
 - Inquire about neuroinflammatory and autoimmune conditions, such as transverse myelitis, uveitis, optic neuritis, and multiple sclerosis. A checklist will be provided as a guide. Please refer to the SRM for additional details.
- Report any SAEs to the sponsor as defined in [Section 8](#).
- Record AEs as described in the AE Reporting Requirements section ([Section 8](#)) and the [Schedule of Activities](#).
- Record nonstudy vaccinations as described in the Concomitant Treatment(s) section ([Section 5.11](#)).
- Record concomitant medications used to treat AEs as described in the Concomitant Treatment(s) section ([Section 5.11](#)).
- Review AEs that were ongoing since the previous visit and record their end dates or confirm that they are still continuing.
- Complete the source documents.
- Complete the CRFs.
- Inform subjects from the ACWY-naïve stratum to expect a telephone contact to confirm if they are able to participate in Stage 2.

6.2.6. Visit 6 (After Study Unblinding and Prior to Transition to Stage 2) Telephone Contact

Visit 6 will be conducted once the sponsor has informed the investigator if the subject may progress to Stage 2 ([Section 5.5.1](#)). Visit 6 must be conducted prior to Visit 7.

- Notify the parent(s)/legal guardian or the subject by telephone if the subject may progress to Stage 2.
- For subjects progressing to Stage 2, schedule an appointment for the next study visit and confirm that it is scheduled within the time window per protocol.

6.3. Stage 2

Subjects from both the ACWY-naïve and ACWY-experienced strata, approximately 132 from each of Groups 1 and 3 and approximately 65 from each of Groups 2 and 4, will participate in Stage 2. Stage 1 will be observer-blinded and Stage 2 will be open-label. Investigators will be informed if a subject can be screened for Stage 2 based on a randomly generated list of eligible subjects and a randomly generated backup list to allow for replacement of subjects who decline participation in Stage 2 or are deemed ineligible after screening at Visit 7.

Visit 7 and Visit 8 should be conducted within no less than 30 days of each other. If Visit 7 cannot be conducted within the protocol-defined visit window, Visit 7 can be omitted and Visit 8 performed directly.

6.3.1. Visit 7 (336 to 694 Days After Visit 3), Antibody Persistence Blood Draw 1

- Obtain written informed consent, and assent if applicable, before performing further study-specific procedures. The date of informed consent will be recorded on the CRF.
- Ensure that the subject continues to be eligible for the study, meets none of the withdrawal criteria as described in [Section 6.5](#), and meets none of the temporary delay of blood draw criteria as described in [Section 4.4](#).
- Record nonstudy vaccinations as described in the Concomitant Treatment(s) section ([Section 5.11](#)).
- Collect a blood sample (approximately 20 mL).
- Record concomitant medications used to treat AEs as described in the Concomitant Treatment(s) section ([Section 5.11](#)).
- Schedule an appointment for the next visit and confirm that it is scheduled within the time window per protocol.
- Complete the source documents.
- Complete the CRFs.

6.3.2. Visit 8 (700 to 756 Days After Visit 3), Antibody Persistence Blood Draw 2

- Ensure that the subject continues to be eligible for the study, meets none of the withdrawal criteria as described in [Section 6.5](#), and meets none of the temporary delay of blood draw criteria as described in [Section 4.4](#).
- Record nonstudy vaccinations as described in the Concomitant Treatment(s) section ([Section 5.11](#)).
- Collect a blood sample (approximately 20 mL).
- Record any AEs and research-related injuries (RRIs) occurring within 48 hours after the Visit 7 blood draw as described in [Section 8](#).
- Record concomitant medications used to treat AEs as described in the Concomitant Treatment(s) section ([Section 5.11](#)).
- Schedule an appointment for the next visit and confirm that it is scheduled within the time window per protocol.
- Complete the source documents.
- Complete the CRFs.

6.3.3. Visit 9 (1064 to 1120 Days After Visit 3), Antibody Persistence Blood Draw 3

- Ensure that the subject continues to be eligible for the study, meets none of the withdrawal criteria as described in [Section 6.5](#), and meets none of the temporary delay of blood draw criteria as described in [Section 4.4](#).
- Record nonstudy vaccinations as described in the Concomitant Treatment(s) section ([Section 5.11](#)).
- Collect a blood sample (approximately 20 mL).
- Record any AEs and RRIs occurring within 48 hours after the Visit 8 blood draw as described in [Section 8](#).
- Record concomitant medications used to treat AEs as described in the Concomitant Treatment(s) section ([Section 5.11](#)).
- Schedule an appointment for the next visit and confirm that it is scheduled within the time window per protocol.
- Complete the source documents.
- Complete the CRFs.

6.3.4. Visit 10 (1428 to 1484 Days After Visit 3): Booster Vaccination

In the case of temporary delay of vaccination, procedures and assessments below will be redone or reconfirmed, as applicable, on the day of vaccination.

- Ensure that the subject continues to be eligible for the study, and continues to comply with contraception requirements detailed in [Section 4.5](#).
- Ensure that the subject continues to meet none of the withdrawal criteria as described in [Section 6.5](#) and none of the temporary delay of vaccination or blood draw criteria as described in [Section 4.3](#) and [Section 4.4](#).
- Record nonstudy vaccinations as described in the Concomitant Treatment(s) section ([Section 5.11](#)).
- Record any antipyretics and other pain medications received by the subject on the day prior to investigational product administration as described in [Section 5.11](#).
- Record the presence of chronic conditions and/or medical history of significance, including relevant surgical procedures and cardiac medical history that have been diagnosed since Visit 1.
- Perform physical examination evaluating any clinically significant abnormalities within the following body systems: general appearance; skin; head, eyes, ears, nose, throat; heart; lungs; abdomen; extremities; neurological; musculoskeletal; and lymph nodes; including worsening of medical history conditions. Results must be recorded on source documents and the CRF. Findings from a physical examination conducted as part of standard routine care and before informed consent may be used for purposes of the study only if the examination was performed no more than 2 days before vaccination. A brief examination must be performed on the day of vaccination to document that no change in health has occurred in the interim.
- On the day of vaccination, perform a urine pregnancy test on female subjects. A negative pregnancy test result is required before the subject may receive the investigational product.
- On the day of and before vaccination, measure and record the subject's oral temperature.
- On the day of and before vaccination, collect a blood sample (approximately 20 mL) from the subject. Collect the blood sample only if the subject is eligible for vaccination on the same day.
- Administer a single 0.5-mL intramuscular injection of either MenABCWY (Groups 1 and 3) or bivalent rLP2086 (Groups 2 and 4) into the upper deltoid muscle of the left arm; and MenACWY-CRM (Groups 2 and 4) into the upper deltoid muscle of the right arm. The time of investigational product administration will be recorded on the CRF.

- Observe the subject for at least 30 minutes (or longer as per local practice) after the investigational product administration for any acute reactions. Record any AEs observed during the 30-minute observation period; these AEs are defined as immediate AEs ([Section 8](#)).
- Record AEs as described in the AE Reporting Requirements section ([Section 8](#)) and the [Schedule of Activities](#). Time of onset will be recorded for any AEs that occur on the same day as investigational product administration.
- Record concomitant medications used to treat AEs as described in the Concomitant Treatment(s) section ([Section 5.11](#)).
- Issue a subject e-diary and provide instruction on its completion. Ask the parent(s)/legal guardian or subject to complete the e-diary from Day 1 to Day 7 after vaccination. Day 1 is the day of vaccination.
- Issue a caliper, measuring tape/ruler, and a digital thermometer and provide instructions on their use.
- Measuring tape/ruler data must be collected by the parent(s)/legal guardian for minor subjects. All data must be recorded in the e-diary by the parent/legal guardian for minor subjects.
- Ask the parent(s)/legal guardian or the subject to use the caliper to measure the maximum diameter of redness and swelling at the left arm injection site each day for the 7 days after study vaccination and record in the e-diary as described in [Section 7.4](#).
- Ask the parent(s)/legal guardian or the subject to contact the investigator immediately if the subject experiences a severe redness or swelling (>20 caliper units) at the left arm injection site, a fever $\geq 39.0^{\circ}\text{C}$ (102.1°F), or a severe headache within 7 days after vaccination, as an unscheduled visit should be arranged ([Section 6.4](#)).
 - If the reaction exceeds the maximum size the caliper is able to measure (>21 caliper units, [Section 7.4.1](#)), the parent/legal guardian or the subject should also use the measuring tape/ruler to measure the maximum diameter of redness and/or swelling at the injection site, and report this immediately to the investigator.
 - Ask the parent(s)/legal guardian or subject to report the maximum diameter of the redness and/or swelling at the injection site to the investigator daily until the reaction becomes ≤ 21 caliper units.
- Ask the parent(s)/legal guardian or the subject to contact the investigator immediately if any significant illness or hospitalization occurs.

- Schedule an appointment for the next study visit and confirm that it is scheduled within the time window per protocol.
- Remind parent(s)/legal guardian or subject to bring the e-diary to the next study visit. Complete the source documents.
- Complete the CRF and update the investigational product accountability records.

Between visits, review the e-diary data online at frequent intervals. Contact the parent(s)/legal guardian or the subject to obtain stop dates for any local reactions, systemic events, or use of antipyretic medication that were ongoing on the last day that the e-diary was completed. The stop dates should be documented in the source documents and the information entered into the CRF at the next study visit of the subject.

6.3.5. Visit 11 (28 to 42 Days After Visit 10), Postbooster Blood Draw

- Ensure that the subject continues to be eligible for the study, and continues to comply with contraception requirements detailed in [Section 4.5](#).
- Ensure that the subject continues to meet none of the withdrawal criteria as described in [Section 6.5](#) and none of the temporary delay of blood draw criteria as described in [Section 4.4](#).
- Collect the subject's e-diary.
- Review the subject's e-diary data since the previous visit and follow up on any ongoing reactogenicity or use of antipyretic medication.
- Complete the Study Visit/Telephone Contact AE Checklist to:
 - Inquire whether the subject had any newly diagnosed chronic medical conditions since the last visit. Inquire whether the subject had any of the following related to an AE since the last visit: hospitalizations, visits to other medical facilities, medication use, or missed days of school or work. Please refer to the SRM for additional details.
 - Inquire about neuroinflammatory and autoimmune conditions, such as transverse myelitis, uveitis, optic neuritis, and multiple sclerosis. Please refer to the SRM for additional details.
- Record AEs as described in the AE Reporting Requirements section ([Section 8](#)) and the [Schedule of Activities](#).
- Review AEs that were ongoing since the previous visit and record their end dates or confirm that they are still continuing.

- Record nonstudy vaccinations as described in the Concomitant Treatment(s) section ([Section 5.11](#)).
- Record concomitant medications used to treat AEs as described in the Concomitant Treatment(s) section ([Section 5.11](#)).
- Provide the parent(s)/legal guardian or the subject with a memory aid. Instruct the subject to use the memory aid between Visits 11 and 12 to remind him or her to review any significant illnesses, hospitalizations, newly diagnosed medical conditions, or visits to a medical facility with study site personnel. The memory aid is not a diary for the collection of reactogenicity. Please refer to the SRM and [Section 7.3](#) for additional details.
- Collect a blood sample (approximately 20 mL). Alternatively, for subjects who have consented to participate in the subset, collect approximately 100 mL of blood.
- Ask the parent(s)/legal guardian or the subject to contact the investigator immediately if any significant illness or hospitalization occurs.
- Schedule a final telephone contact and confirm that it is scheduled within the time window per protocol.
- Complete the source documents.
- Complete the CRFs.

6.3.6. Visit 12 (168 to 196 Days After Booster Vaccination), Final Telephone Contact

- The final telephone contact should occur approximately 6 months after the booster vaccination; this contact should be attempted for all subjects who have received the booster vaccination, unless they have withdrawn consent.
- Contact the parent(s)/legal guardian or the subject by telephone.
- Complete the Study Visit/Telephone Contact AE Checklist to:
 - Inquire about SAEs, newly diagnosed chronic medical conditions, or AEs that resulted in evaluation at a medical facility since the last visit. Please refer to the SRM for additional details.
 - Inquire about neuroinflammatory and autoimmune conditions, such as transverse myelitis, uveitis, optic neuritis, and multiple sclerosis. Please refer to the SRM for additional details.
- Report any SAEs to the sponsor as defined in [Section 8](#).

- Record AEs as described in the AE Reporting Requirements section ([Section 8](#)) and the [Schedule of Activities](#).
- Record concomitant medications used to treat AEs as described in the Concomitant Treatment(s) section ([Section 5.11](#)).
- Review AEs that were ongoing since the previous visit and record their end dates or confirm that they are still continuing.
- Complete the source documents.
- Complete the CRFs.

6.4. Unscheduled Visits

If the subject experiences a severe redness or swelling at the left arm injection site (>20 caliper units), a temperature $\geq 39.0^{\circ}\text{C}$ (102.1°F), or a severe headache in the 7 days after vaccination, a study site visit should be arranged as soon as possible to assess the extent of the event. The parent(s)/legal guardian or subject contact will be documented in the CRF.

If the reaction exceeds the maximum size the caliper is able to measure (>21 caliper units, [Section 7.4.1](#)), ensure the parent(s)/legal guardian or subject has also measured the maximum diameter of the redness and/or swelling at the injection site using the measuring tape/ruler provided. Ask the parent(s)/legal guardian or subject to report the maximum diameter of the redness and/or swelling at the injection site daily until the reaction becomes ≤ 21 caliper units. Record these measurements in the CRF.

At an unscheduled visit, the subject's oral temperature should be measured and the symptom that prompted the visit should be assessed by a medically qualified member of the study staff. Findings will be recorded on the CRF. If the subject experiences any unsolicited AEs, these should be recorded on the AE CRF.

If the unscheduled visit does not take place following subject report of fever $\geq 39.0^{\circ}\text{C}$, severe redness/swelling, or severe headache, the reason must be documented in the CRF (for example, reaction no longer present or e-diary entry error).

For the purpose of assessments performed during unscheduled visits, a medically qualified member of the study staff is a study physician or a study nurse, as applicable to the investigator's local practice.

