##### **3.1.2. Primary Safety Endpoints**

The following endpoints will be described after Vaccinations 1 and 2 in the bivalent rLP2086 arms (Group 2 and 4 subjects) combined.

- Percentage of subjects reporting local reactions (pain, redness, and swelling) and by severity within 7 days after each vaccination visit.
- Percentage of subjects reporting systemic events (fever, vomiting, diarrhea, headache, fatigue, chills, muscle pain other than muscle pain at any injection site, and joint pain) and by severity within 7 days after each vaccination visit.
- Percentage of subjects reporting the use of antipyretic medications within 7 days after each vaccination visit.

- Percentage of subjects with at least 1 SAE during the following time periods:
  - 30 Days after each vaccination
  - 30 Days after any vaccination
  - During the Stage 1 vaccination phase (from the first study vaccination [Visit 1] through 1 month after the second study vaccination [Visit 4])
  - During the Stage 1 follow-up phase (from 1 month after the second study vaccination [Visit 4] through 6 months after the second study vaccination [Visit 5])
  - Throughout Stage 1 (from the first study vaccination [Visit 1] through 6 months after the second study vaccination [Visit 5])
  
- Percentage of subjects with at least 1 MAE occurring during the following time periods:
  - 30 Days after each vaccination
  - 30 Days after any vaccination
  - During the Stage 1 vaccination phase (from the first study vaccination [Visit 1] through 1 month after the second study vaccination [Visit 4])
  - During the Stage 1 follow-up phase (from 1 month after the second study vaccination [Visit 4] through 6 months after the second study vaccination [Visit 5])
  - Throughout Stage 1 (from the first study vaccination [Visit 1] through 6 months after the second study vaccination [Visit 5])
  
- Percentage of subjects with at least 1 NDCMC occurring during the following time periods:
  - 30 Days after each vaccination
  - 30 Days after any vaccination
  - During the Stage 1 vaccination phase (from the first study vaccination [Visit 1] through 1 month after the second study vaccination [Visit 4])
  - During the Stage 1 follow-up phase (from 1 month after the second study vaccination [Visit 4] through 6 months after the second study vaccination [Visit 5])
  - Throughout Stage 1 (from the first study vaccination [Visit 1] through 6 months after the second study vaccination [Visit 5])

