### 3.5.2. Reactogenicity Data

The reactogenicity data collected from the study e-diary will include local reactions (redness, swelling, and pain at the injection site) and systemic events (fever, vomiting, diarrhea, headache, fatigue, chills, muscle pain other than muscle pain at the injection site, and joint pain) and use of antipyretic medication.

Reactogenicity data will be recorded in the e-diary from the day of each vaccination (Day 1), following investigational product administration, to Day 7. Local reactions will be collected only for the left arm, which is the MenABCWY or bivalent rLP2086 injection site. See Table 8.

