**Table 9. Derived Variables for Local Reactions**

Variable	Yes (1) a	No (0) b	Missing (.)
Each day (Days 1 to 7)	Subject/parent/legal guardian reports the reaction as “mild,” “moderate,” or “severe” on each individual day.	Subject/parent/legal guardian reports the reaction as “none” on the individual day.	Subject/parent/legal guardian did not report on the reaction on the individual day.
Any day (Days 1 to 7)	Subject/parent/legal guardian reports the reaction as “mild,” “moderate,” or “severe” on any Day 1-7.	Subject/parent legal guardian reports the reaction as “none” on all 7 days or as a combination of “none” and missing on all 7 days.	Subject/parent/legal guardian did not report on the reaction on any of the 7 days.

- a. For redness and swelling, “mild,” “moderate,” or “severe” categories are based on the caliper size reported in the e-diary and as defined in Table 10.
- b. For redness and swelling, “none” means 0 to 4 caliper units reported in the e-diary.

A caliper (measuring device) is used to measure the redness or swelling of the injection site area. Caliper units (range: 1-21+) are converted to cm, with 1 caliper unit equal to 0.5 cm, then categorized as none, mild, moderate, or severe based on the grading scale in Table 10. Pain at the injection site will be assessed by the subject/parent/legal guardian according to the grading scale in Table 11.

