### Maximum Severity for Local Reaction

The maximum severity (highest grading) of each local reaction within 7 days of vaccination will be derived for each vaccination as well as any vaccination. The maximum severity will be derived as follows:

- = ., if values are missing for all Days 1-7;
- = 0, if the subject/parent/legal guardian reports all reactions as ‘none’ or a combination of missing and ‘none’ for all Days 1-7;
- = *highest grade* (maximum severity) within 7 days of vaccination, if the answer is not ‘none’ for at least 1 day.

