**Table 12. Grading of Systemic Events**

	Grade 1 (Mild)	Grade 2 (Moderate)	Grade 3 (Severe)
Vomiting	1 to 2 times in 24 hours	>2 times in 24 hours	Requires IV hydration
Diarrhea	2 to 3 loose stools in 24 hours	4 to 5 loose stools in 24 hours	6 or more loose stools in 24 hours
Headache	Does not interfere with activity	Some interference with activity	Prevents daily routine activity
Fatigue	Does not interfere with activity	Some interference with activity	Prevents daily routine activity
Chills	Does not interfere with activity	Some interference with activity	Prevents daily routine activity
Muscle pain (other than muscle pain at the injection site)	Does not interfere with activity	Some interference with activity	Prevents daily routine activity
Joint pain	Does not interfere with activity	Some interference with activity	Prevents daily routine activity

Abbreviation: IV = intravenous.

Severe vomiting will be queried and if confirmed as an error will be excluded from the analysis.

Oral temperature will be recorded in the e-diary, in the evening, daily for 7 days after each vaccination and at any time during the 7 days when fever is suspected. The highest temperature for each day will be recorded as well. The protocol defines fever as an oral temperature  $\geq 38.0^{\circ}\text{C}$  ( $\geq 100.4^{\circ}\text{F}$ ), with severity scales shown in Table 13 and Table 14.

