**Table 14. Severity Scale for Fever for Stage 2**

38.0-38.4°C
>38.4-38.9°C
>38.9-40.0°C
>40.0°C

Temperatures <35.0°C and >42.0°C will be excluded from the analysis.

The original temperature scale (Table 13) was used in Stage 1 reporting and the updated temperature scale (Table 14) will be used in Stage 2 analyses.

For each systemic event, the following variables will be available similar to local reactions:

1. Each systemic event on each day (Days 1 to 7) after each vaccination.
2. Each systemic event on any day (Days 1 to 7) after each vaccination and any vaccination.
3. Any systemic event on any day (Days 1 to 7) after each vaccination and after any vaccination.
4. Maximum severity of each systemic event on any day (Days 1 to 7) after each vaccination and any vaccination.
5. Maximum duration of each systemic event after each vaccination.

The derivation of these variables is similar to the derivation of the variables for local reactions (Section 3.5.2.1).

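### A severe redness, swelling or headache entry, or a fever of 39.0–42.0°C, that the CRF records as an e-diary error still counts in the primary reactogenicity endpoints, because the SAP excludes confirmed errors only for severe vomiting

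*Protocol*

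**What the plan says.** **Protocol 6.4 (Unscheduled Visits).** Three kinds of report in the 7 days after vaccination trigger a site visit: severe redness or swelling, a temperature of at least 39.0°C, and severe headache. Findings at the visit go on the CRF. If the visit does not happen, "the reason must be documented in the CRF (for example, reaction no longer present or e-diary entry error").

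**SAP 3.5.2 (Reactogenicity Data).** The source for these endpoints is the diary: "The reactogenicity data collected from the study e-diary will include local reactions", together with the systemic events.

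**SAP 3.5.2.1.** In Table 9, the any-day variable for a local reaction is positive when the condition "Subject/parent/legal guardian reports the reaction as “mild,” “moderate,” or “severe” on any Day 1-7" is met. Maximum severity is the highest grade ("maximum severity) within 7 days of vaccination, if the answer is not ‘none’ for at least 1 day"). SAP 3.5.2.2 carries both rules over to systemic events: "The derivation of these variables is similar to the derivation of the variables for local reactions".

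**Exclusions.** SAP 3.5.2.2 has two. Under Table 12: "Severe vomiting will be queried and if confirmed as an error will be excluded from the analysis". Under Table 14: "Temperatures <35.0°C and >42.0°C will be excluded from the analysis".

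**Endpoint.** SAP 3.1.2 lists, for Groups 2 and 4 combined after Vaccinations 1 and 2, "Percentage of subjects reporting local reactions (pain, redness, and swelling) and by severity within 7 days after each vaccination visit". It has a matching endpoint for systemic events and repeats both after the booster for Groups 1 through 4. SAP 5.3.2.1 plans no sensitivity analysis for reactogenicity.

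**The concern.** The protocol foresees that some severe or high-fever entries will be mistakes and has the site record this on the CRF. The SAP accepts in principle that a confirmed mistake should not be analysed, since it says so for vomiting. It does not extend that to the three events for which the protocol collects the evidence.

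One false severe day is enough to classify a subject as severe, because the derivation takes the highest grade over seven days. Severe categories are usually small, so a few such entries could visibly change the reported percentage. SAP 5.2.1.3 says the safety intervals will help decide which events need further clinical investigation. The booster tables are the most exposed, because their denominators are smallest.

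**Working it through.** The plan gives no figure on this point to reproduce. The check is a comparison of texts, followed by arithmetic for scale.

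**Step 1. Follow-up against exclusion, item by item.**

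| Diary item | Triggers follow-up under Protocol 6.4 | Exclusion in SAP 3.5.2 |
|---|---|---|
| Severe redness or swelling | Yes | None |
| Severe headache | Yes | None |
| Fever of at least 39.0°C | Yes | Only above 42.0°C |
| Severe vomiting | No | Excluded if error confirmed |
| Severe pain, diarrhea, fatigue, chills, muscle pain, joint pain | No | None |

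The items with a CRF route for recording an entry error are not the item with a rule that acts on one. The temperature limits are plausibility cut-offs. They do not use the CRF reason and they keep a false 39.0–42.0°C.

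**Step 2. Effect of one false entry.** Assume the subject has no other entry that severe for the item in the 7 days. The percentage then rises by 100 × 1/N. The planned denominators are in Protocol 9.1 (about 1060 in Groups 2 and 4) and SAP 2.2.1 (booster: about 264 in Groups 1 and 3, about 130 in Groups 2 and 4).

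- Stage 1, Groups 2+4: 100 × 1/1060 = 0.09 points
- Booster, Groups 1+3: 100 × 1/264 = 0.38 points
- Booster, Groups 2+4: 100 × 1/130 = 0.77 points
- Booster, Group 2 or Group 4 alone (about 65): 100 × 1/65 = 1.5 points

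**Step 3. Illustration with intervals.** The documents give neither the true number of severe cases nor the number of errors, so both are assumed. The intervals are Clopper-Pearson, as in SAP 5.2.1.1. For r cases in N, the lower limit is the 2.5th percentile of Beta(r, N−r+1) and the upper limit is the 97.5th percentile of Beta(r+1, N−r).

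| N | True cases (assumed) | No false entry, % (95% CI) | 1 false entry | 3 false entries |
|---|---|---|---|---|
| 1060 | 5 | 0.47 (0.15, 1.10) | 0.57 (0.21, 1.23) | 0.75 (0.33, 1.48) |
| 1060 | 11 | 1.04 (0.52, 1.85) | 1.13 (0.59, 1.97) | 1.32 (0.72, 2.21) |
| 1060 | 21 | 1.98 (1.23, 3.01) | 2.08 (1.31, 3.13) | 2.26 (1.46, 3.35) |
| 264 | 3 | 1.14 (0.23, 3.28) | 1.52 (0.41, 3.83) | 2.27 (0.84, 4.88) |
| 130 | 1 | 0.77 (0.02, 4.21) | 1.54 (0.19, 5.45) | 3.08 (0.84, 7.69) |

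In relative terms, 1 to 3 errors on 11 true cases is 1/11 to 3/11, or 9% to 27%. On 21 true cases it is 1/21 to 3/21, or 5% to 14%. In every row shown, the intervals with and without the false entries overlap widely.

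**The case against.** **The endpoint is what subjects report.** Protocol 7.4 restricts diary entry to a fixed time window so that entries reflect the experience at the time. Removing severe reports later on the site's word can only lower severe rates, and in open-label Stage 2 the site knows the vaccine. This stands, and it is why the as-entered table should remain the main analysis.

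**Errors may be removed elsewhere.** SAP 7.4.3 mentions data cleaning, Protocol 11.1 allows documented corrections to CRF and source entries, and SAP section 2 refers to separate programming rules. A reader might infer that known false entries certainly remain in the final data. The documents do not prove that, because the programming rules were not available. But none of these places states a rule for correcting the e-diary, so the SAP followed as written counts the entry.

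**Severe entries are visible anyway.** SAP 6.7.1 promises a listing of all severe reactions. That helps a reader of the listing but does not change the percentages.

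**The vomiting rule may be deliberate.** Severe vomiting has no follow-up under Protocol 6.4, so a separate query for it is understandable. That does not explain why the CRF reason for the other events is unused.

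**A severe reaction could also be missed.** A reader might infer that severe reactions seen at unscheduled visits are being lost, since Table 9 codes a mix of missing days and days without a reaction as no reaction. This is possible under the wording. But SAP 5.3.2.1 expects minimal missing data, and nothing in the documents suggests such cases are frequent.

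**Conclusion.** The gap is real and minor. For the Protocol 6.4 triggers, an entry that the CRF documents as a diary error would, under the SAP as written, count as a severe or high-grade case. The endpoints affected are primary for Groups 2+4 in Stage 1 and for all groups after the booster; Stage 1 severity rates for Groups 1+3 are secondary. The consequence is upward bias in descriptive percentages. No hypothesis test or decision rule depends on it.

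The per-entry effects follow from the planned denominators. Any total effect rests on assumed error and event counts.

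Two broader readings are tempting and go too far. One is that sites must document every diary error: the reason is required only when no visit takes place, and entry error is only an example of a reason. The other is that one verification rule could cover all diary items: existing CRF data support it only for redness, swelling, headache and fever.

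**What to change.** In SAP 3.5.2:

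1. Keep the as-entered e-diary table as the main analysis.
2. For severe redness or swelling, severe headache and fever of at least 39.0°C only, add a supplementary booster (Stage 2) summary. In it, set to missing, for that item and day, each entry that the CRF documents as a diary entry error. A reaction that had merely resolved before a visit could be arranged is not an error and stays in.
3. Give the number of entries changed, by group.
4. List separately any severe finding recorded on the CRF at an unscheduled visit on a day with no diary entry. Do not merge these into the diary grades, because that would mix staff assessment with subject report.
5. Label any re-run for Stage 1 as supplementary and post hoc. SAP 3.5.2.2 shows that Stage 1 has already been reported.

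If the separate programming rules already handle these entries, one SAP sentence saying how would close the question.

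The cost is a short SAP addition and one summary from CRF data the protocol already requires. The downside is one extra table to explain.
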